### **3.3 SELECTION OF TRIAL POPULATION**

Approximately 12 patients are planned to be included, but will be adjusted by DLT results. This trial will be conducted in Japan and provide the safety and PK data in Japanese patients in multiple dose levels.

A log of all patients enrolled into the trial (i.e. who have signed informed consent) will be maintained in the Investigator Site File (ISF) irrespective of whether they have been treated with investigational drug or not.

If a patient is enrolled in error (does not meet all inclusion criteria or meets one or more exclusion criteria on the day of enrolment), the sponsor should be contacted immediately.

### 3.3.1 Main diagnosis for trial entry

Patients with a confirmed diagnosis of NRAS or KRAS mutation positive advanced, unresectable and/or metastatic solid tumours, who have failed standard treatment(s), or for whom no therapy of proven efficacy exists, or who are not amenable to standard therapies.

Please refer to [section 8.3.1](#) (Source Documents) for the documentation requirements pertaining to the in- and exclusion criteria.

### 3.3.2 Inclusion criteria

1. Must be at least 20 years of age at screening.
2. Signed and dated written informed consent in accordance with GCP and local legislation prior to admission to the trial.
3. Pathologically documented, locally-advanced or metastatic malignancy with previously identified activating NRAS or KRAS mutation based on local test.
4. Provision of archival tumor tissue, if available, to confirm retrospectively NRAS or KRAS mutation status and for biomarker assessment.
5. Willingness to undergo pre- and on-treatment tumour biopsies [REDACTED]. Patients can be enrolled without tumour biopsy upon agreement between the Investigator and the Sponsor if tumour biopsy is not feasible (Apply only to study site which agreed to conduct biopsy).
6. Must have either progressed despite appropriate prior standard therapies or for whom no standard therapy exists for their tumour type and disease stage
7. Must have at least one target lesion that can be measured per RECIST version 1.1
8. Must have an Eastern Cooperative Oncology Group (ECOG) performance status of 0 or 1.
9. Must show adequate organ function as follows:
  - a) Absolute neutrophil count (ANC)  $\geq 1.5 \times 10^9/L$ ; hemoglobin  $\geq 9.0 \text{ g/dL}$ ; platelets  $\geq 100 \times 10^9/L$  without the use of hematopoietic growth factors.
  - b) Total bilirubin  $\leq 1.5$  times the ULN, or  $\leq 4 \times \text{ULN}$  for patients who are known to have Gilbert's syndrome.
  - c) Creatinine  $\leq 1.5 \times \text{ULN}$ . If creatinine is  $>1.5 \times \text{ULN}$ , patient is eligible if concurrent creatinine clearance  $\geq 50 \text{ mL/min}$  (measured or calculated by Chronic Kidney Disease Epidemiology [CKD-EPI] formula).
  - d) AST and ALT  $\leq 3 \times \text{ULN}$  if no demonstrable liver metastases, or otherwise  $\leq 5 \times \text{ULN}$ .
10. Creatine phosphokinase is  $<2.5 \times \text{ULN}$ .
11. Must have recovered from any previous therapy related toxicity to Common Terminology Criteria for Adverse Events (CTCAE) grade  $\leq 1$  at C1V1 (except for alopecia; stable sensory neuropathy must be CTCAE grade  $\leq 2$ ).
12. Male patients able to father a child and/or female patients of childbearing potential must be able and willing to comply with contraceptive measures i.e. use highly effective methods of birth control per ICH M3 (R2) that result in a low failure rate of less than 1% per year when used consistently and correctly, prior to study entry and for the duration of study participation and for a minimum timeperiod after treatment has ended, at least 3 months.
13. Women of childbearing potential who are not surgically sterilized must have a negative serum pregnancy test completed during the Screening period.

Proprietary confidential information © 2020 Boehringer Ingelheim International GmbH or one or more of its affiliated companies

14. Women who are nursing. Women who are nursing can be enrolled if they stop nursing. In this case, the patient cannot resume nursing until 30 days from discontinuation of study treatment.

\*A woman is considered of childbearing potential (WOCBP), i.e. fertile, following menarche and until becoming post-menopausal unless permanently sterile.

Permanent sterilisation methods include hysterectomy, bilateral salpingectomy and bilateral oophorectomy. Tubal ligation is NOT considered as a method of permanent sterilisation.

A postmenopausal state is defined as no menses for 12 months without an alternative medical cause. Addition to this, even no menses for 12 months, if possibility of amenorrhea caused by anti tumor treatment can not be denied, pregnancy test should be conducted as same as WOCBP.

### 3.3.3 Exclusion criteria

1. Previous anticancer chemotherapy within 3 weeks of the first administration of trial drug. Previous anticancer hormonal treatment or anticancer immunotherapy within 2 weeks of the first administration of trial drugs.
2. Radiotherapy within 4 weeks prior to first administration of BI 3011441 except as follows
  - Palliative radiotherapy to regions other than the chest is allowed up to 2 weeks prior to start of treatment
  - Single dose palliative radiotherapy for symptomatic metastasis within 2 weeks prior to start of treatment may be allowed but must be discussed with the sponsor.
3. Major surgery within 4 weeks prior to start of treatment or scheduled during the projected course of the trial
4. Previous treatment with a RAS, MAPK targeting agent
5. Previous treatment with any investigational agent(s) or targeted treatment within 4 weeks (28 days) prior to start of trial drug or concurrent participation in another clinical trial with an investigational device or drug.
6. Any history of or concomitant condition that, in the opinion of the investigator, would compromise the patient's ability to comply with the study or interfere with the evaluation of the efficacy and safety of the study medications
7. Patients who have a history or current evidence/risk of retinal vein occlusion (RVO) or retinal pigment epithelial detachment or central serous retinopathy; for example, predisposing factors of RVO or central serous retinopathy include uncontrolled glaucoma or ocular hypertension, history of hyperviscosity or hypercoagulability syndromes.
8. Patients who have visible retinal pathology that is considered a risk factor for RVO or central serous retinopathy as assessed by ophthalmic examination, such as:
  - Evidence of new optic disc cupping
  - Evidence of new visual field defects
  - Intraocular pressure >21 mm Hg

History or presence of cardiovascular abnormalities such as uncontrolled hypertension, congestive heart failure NYHA classification of  $\geq 2$ , unstable angina or poorly controlled arrhythmia which are considered as clinically relevant by the investigator; Myocardial infarction within 6 months prior to start of treatment. Uncontrolled hypertension is defined

Proprietary confidential information © 2020 Boehringer Ingelheim International GmbH or one or more of its affiliated companies

as: Blood pressure measured in a rested and relaxed condition, where systolic BP  $\geq 140$  mmHg, or diastolic BP  $\geq 90$  mmHg, with or without medication.

9. Left ventricular ejection fraction (LVEF)  $< 50\%$ .
10. Baseline QT interval corrected for heart rate using Fridericia's formula (QTcF)  $> 470$  msec or congenital long QT syndrome
11. Previous or concomitant malignancies at other sites, except effectively treated
  - Non-melanoma skin cancers
  - Carcinoma *in situ* of the cervix
  - Ductal carcinoma *in situ*
  - Other malignancy that has been in remission for more than 3 years and is considered to be cured.
12. Leptomeningeal carcinomatosis.
13. Presence or history of uncontrolled or symptomatic brain metastases, unless considered stable by the investigator and local therapy was completed. Use of corticosteroids is allowed if the dose was stable for at least 4 weeks. Inclusion of patients with newly identified brain metastasis/es at screening will be allowed if patients are asymptomatic.
  - Patients who have resected brain metastases, or have received radiation therapy that finished at least 4 weeks (whole brain radiation) or 2 weeks (stereotactic body radiotherapy) prior to treatment of the trial are considered eligible if they meet all of the following criteria:
    - a) Residual neurological symptoms CTCAE grade  $\leq 2$
    - b) Are taking stable doses of dexamethasone, if applicable
    - c) Follow-up magnetic resonance imaging (MRI) shows no new lesions
14. Known pre-existing interstitial lung disease
15. Known active hepatitis B infection (defined as presence of Hep B sAg and/or Hep B DNA), active hepatitis C infection (defined as presence of Hep C RNA)
16. Active infectious disease which puts the patient at increased risk in the opinion of the investigator
17. Any history or presence of uncontrolled gastrointestinal disorders that could affect the intake and/or absorption of the study drug (e.g. nausea, uncontrolled vomiting, Crohn's disease, ulcerative colitis, chronic diarrhoea, malabsorption) in the opinion of the investigator.
18. Patients not expected to comply with the protocol requirements or not expected to complete the trial as scheduled (e.g. chronic alcohol or drug abuse or any other condition that, in the investigator's opinion, makes the patient an unreliable trial participant).

### 3.3.4 Withdrawal of patients from treatment or assessments

Patients may discontinue trial treatment or withdraw consent to trial participation as a whole ("withdrawal of consent") with very different implications; please see [sections 3.3.4.1](#) and [3.3.4.1.1](#) below.

Every effort should be made to keep the patients in the trial: if possible on treatment, or at least to collect important trial data.

Proprietary confidential information © 2020 Boehringer Ingelheim International GmbH or one or more of its affiliated companies

Measures to control the withdrawal rate include careful patient selection, appropriate explanation of the trial requirements and procedures prior to trial enrolment, as well as the explanation of the consequences of withdrawal.

The decision to discontinue trial treatment or withdraw consent to trial participation and the reason must be documented in the patient files and Case report form (CRF). If applicable, consider the requirements for Adverse Event collection reporting (please see [sections 5.2.6.2.1](#) and [5.2.6.2](#)).

### **3.3.4.1 Discontinuation of trial treatment**

An individual patient will discontinue trial treatment if:

- The patient wants to discontinue trial treatment, without the need to justify the decision.
- The patient has repeatedly shown to be non-compliant with important trial procedures and, in the opinion of both, the investigator and sponsor representative, is not willing or able to adhere to the trial requirements in the future.
- The patient needs to take concomitant medication that interferes with the investigational medicinal product or other trial treatment
- The patient becomes pregnant. The patient can no longer receive trial treatment for medical reasons (such as surgery, adverse events or other diseases).

BI 3011441 should be permanently discontinued in case of :

- Retinal vein occlusion (RVO)
- Symptomatic heart failure
- Interstitial lung disease/pneumonitis, regardless of grade
- Recurrent Grade 4 AEs or persistent Grade 2 to 3 AEs that do not recover to Grade 1 or less within 12 weeks
- Drug-related Grade 4 AEs.

An interruption of treatment or delayed start of treatment of more than 4 weeks or several interruptions exceeding a total of  $\geq 28$  days of BI 3011441 treatment due to SAEs/AEs will lead to permanent treatment discontinuation. However in well-justified cases if considered clinically indicated by the Investigator and aligned with the Sponsor (to be documented in writing), a patient can be re exposed to treatment.

In case of a temporary reason, trial treatment should be restarted if medically justified, please see [section 4.1.4](#).

If new efficacy/safety information of BI 3011441 becomes available, Boehringer Ingelheim (BI) will review the benefit-risk-assessment and, if needed, pause or discontinue the trial treatment for all patients or take any other appropriate action to guarantee the safety of the trial patients.

Even if the trial treatment is discontinued, the patients remain in the trial and, given their agreement, will undergo the procedures for early treatment discontinuation and follow-up as outlined in the [Flow Chart](#) and [section 6.2.3](#).

### 3.3.4.1.1 Enrolment stopping rules

All safety information will be carefully analysed by the sponsor. Enrolment will be temporarily stopped if clinically relevant adverse events occur which meet both of the following criteria:

- Clinically relevant adverse events that:
  - are associated with evidence suggesting a reasonable possibility that the investigational drug caused the adverse event; and
  - occur at frequency or with severity that suggest that the risk-benefit profile of the study drug(s) should be reassessed.

If the SMC determines that the above criteria are met the enrolment to the trial will be temporarily stopped to allow for in-depth analysis of the safety profile of BI 3011441. The benefit-risk profile of BI 3011441 will be re-assessed by the SMC. This assessment will be used to determine if the trial should be continued as planned, permanently discontinued or whether the trial should continue with modification to the protocol. The purpose of any modifications to the protocol will be to mitigate patient risk and ensure that the benefit-risk assessment for continued investigation of BI 3011441 remains positive. The SMC will also consider and provide guidance for the management of patients who are already receiving treatment. The outcome of the analysis and the recommendations will be shared with all involved regulatory health authorities prior to a planned re-start of enrolment. In case the benefit-risk assessment is no longer considered to be positive, the trial will be discontinued.

### 3.3.4.1.2 Replacement of patients

Patients who are not evaluable for the MTD determination will be replaced, and an additional patient will be entered at the same dose level, if not decided otherwise by the SMC (e.g. because the number of evaluable patients for the current dose level is considered high enough for a dose escalation decision).

Patients who permanently discontinue treatment because of a DLT (please see [section 5.2.6.3](#)) will not be replaced.

The following patients may be replaced:

- Patients who have not received any drug after they have signed the informed consent.
- Patients who permanently discontinue treatment during the MTD evaluation period for reasons other than a DLT.
- Patients who have missed more than 8 doses of BI 3011441 during the MTD evaluation period for reasons other than a DLT.
- Patients who miss 2 or more partial or complete visits during the MTD evaluation period and (after discussion between the Sponsor and the Investigator) if the information needed to assess PK/PD and safety parameters (including evaluation for DLTs) is missing, unless they develop a DLT.
- Patient who need palliative radiotherapy during MTD determination period (e.g. first 4 weeks).

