#### 2.1.2 Primary endpoint(s)

- MTD defined as the highest dose with less than 25% risk of the true DLT rate being equal or above 33% during the MTD evaluation period. For the definition of DLTs, refer to [Section 5.2.6.3](#)
- Number of patients with DLTs in the MTD evaluation period.

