## 7. STATISTICAL METHODS AND DETERMINATION OF SAMPLE SIZE

### 7.1 STATISTICAL DESIGN – MODEL

The trial will be performed as an open-label trial. The objective of the design is to determine the MTD defined as the highest dose with less than 25% risk of the true DLT rate being equal or above 0.33 (EWOC criterion). The phase I dose-finding will be guided by a Bayesian 2-parameter logistic regression model with overdose control ([R13-4806](#); [R13-4803](#)).

The model is given as follows:

$$\text{logit}(\pi_d) = \log(\alpha) + \beta * \log(d/d^*),$$

where  $\text{logit}(\pi) = \log(\pi/(1-\pi))$ .

$\pi_d$  represents the probability of having a DLT in the MTD evaluation period at dose  $d$ ,  $d^* = 8$  mg is the reference dose, allowing for the interpretation of  $\alpha$  as the odds of a DLT at dose  $d^*$ , and  $\theta = (\log(\alpha), \log(\beta))$  with  $\alpha, \beta > 0$  is the parameter vector of the model. The estimated probability of a DLT at each dose level from the model will be summarized using the following intervals:

Under toxicity: [0.00, 0.16)

Targeted toxicity: [0.16, 0.33)

Over toxicity: [0.33, 1.00]

The BLRM-recommended dose for the next cohort is the level with the highest posterior probability of the DLT rate falling in the target interval [0.16, 0.33) among the doses fulfilling EWOC. Applying the EWOC criterion, it should be unlikely (<25% posterior probability) that the DLT rate at that dose will exceed 0.33. However, the maximum allowable dose increment for the subsequent cohort will be no more than 50 % for each dose level.

The MTD may be considered reached if one of the following criteria is fulfilled:

1. The posterior probability of the true DLT rate in the target interval [0.16 – 0.33) of the MTD is above 0.5, OR
2. At least 12 patients have been treated in the dose escalation phase of the trial, of which at least 6 at the MTD.

The SMC may recommend stopping the dose escalation phase after the criterion for MTD is fulfilled. Further patients may be included to confirm this MTD estimate. If no DLT is observed at a dose of which the efficacy is considered sufficient, the SMC may decide to include an additional number of patients at this dose level and to declare this dose as the dose recommended for further testing

Since a Bayesian approach is applied, a prior distribution  $f(\theta)$  for the unknown parameter vector  $\theta$  needs to be specified.

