### 7.3.2 Primary endpoint analyses

In order to identify the MTD, the number of evaluable patients with DLTs during the MTD evaluation period at each dose level must be presented. Replaced patients will be excluded from the determination of MTD.

The main analysis of the MTD will use the BLRM model described above using DLT data from the MTD evaluation period.

For the analysis of tolerability and safety, please refer to [Section 7.3.5](#).

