6.3 SUBJECT SETS ANALYSED

- Screened Set:

This subject set includes all patients who have signed the informed consent. The screened set is used for patient disposition tables.

- Treated Set (TS):

This subject set includes all patients who were dispensed study medication and were documented to have taken at least one dose of investigational treatment. The treated set is used for both efficacy analyses and safety analyses.

- MTD Set:

This subject set includes all patients evaluable for MTD in the dose escalation part of the trial, who were not replaced within the MTD evaluation period. Replaced patients will also be included (refer to CTP Section 3.3.4.1.2 for criteria for being evaluable for MTD). The MTD set will be used for Bayesian Logistic Regression Models (BLRMs).

- PK Analysis Set (PKS):

This subject set includes all patients in the treated set who provided at least one evaluable observation for at least one PK endpoint and were not excluded due to a protocol deviation relevant to the evaluation of PK or due to PK non-evaluability. Analyses of PK parameters will be based on the PKS. The PKS will be used for statistical pharmacokinetic analyses.

Plasma concentrations and/or parameters of a patient will be considered as nonevaluable, if for example

- 1) The patient experienced emesis that occurred at or before two times median t_{max} of the respective treatment (Median t_{max} is to be determined excluding the patients experiencing emesis),
- 2) A predose concentration is $>5\%$ C_{max} value of that patient in the respective treatment period
- 3) Missing samples/concentration data at important phases of PK disposition curve

■ [REDACTED]

[REDACTED]

[REDACTED]

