7.8 SAFETY ANALYSIS

All safety analyses will be performed on the treated set. Treated patients will be analyzed according to their initial treatment.

Patients who were replaced within the MTD evaluation period will be excluded from the determination of the MTD in the dose escalation but will be considered for all other safety evaluations.

Safety data recorded during the Residual Effect Period (REP) of 30 days will be considered as on-treatment.

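### The BLRM is limited to MTD-evaluable patients, but neither document defines that term, and SAP 6.3 contradicts itself on whether replaced patients count

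*Protocol*

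**What the plan says.** **Who enters the model.** Protocol 7.3.1 and SAP 7.4.1 restrict the MTD determination to MTD-evaluable patients. Neither gives criteria.

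**Where the criteria should be.** The MTD Set definition in SAP 6.3 tells the reader to "refer to CTP Section 3.3.4.1.2 for criteria for being evaluable for MTD". Protocol 3.3.4.1.2 opens by saying that non-evaluable patients are replaced unless the SMC decides otherwise, for example "because the number of evaluable patients for the current dose level is considered high enough for a dose escalation decision". It then gives a list under the words "The following patients may be replaced": never dosed, permanent stop in the MTD evaluation period for a reason other than a DLT, more than 8 missed doses, missed visits with the needed information missing, and palliative radiotherapy. The list is not labelled as a list of non-evaluable patients.

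**Who is excluded.** Protocol 7.3.2: "Replaced patients will be excluded from the determination of MTD". SAP 7.8: "Patients who were replaced within the MTD evaluation period will be excluded from the determination of the MTD". Both are worded by replacement. SAP 6.3 first requires a patient to be evaluable and not replaced, and in the next sentence says that replaced patients are in the set as well.

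**What the set decides.** The primary endpoint is the "MTD defined as the highest dose with less than 25% risk of the true DLT rate being equal or above 33" percent. Within that limit, the dose the model recommends "is the level with the highest posterior probability of the DLT rate falling in the target interval" (Protocol 7.1).

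**The concern.** The primary endpoint depends on a set whose membership cannot be read from the text. A programmer who follows the SAP's pointer finds a list of patients whom the SMC may or may not replace, and two consecutive sentences of SAP 6.3 give opposite instructions on those who are replaced.

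That leaves two routes by which a patient with incomplete treatment and no DLT could be counted as a full DLT-free observation:

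- **Replaced patient.** SAP 6.3, read literally, adds the patient back beside the replacement.
- **Unreplaced patient.** No stated test says whether a listed patient whom the SMC chooses not to replace is evaluable. The judgement falls to a committee of participating investigators and sponsor trial-team members (Protocol 8.7) in an open-label trial, after the outcome is known.

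Either route adds to the denominator and nothing to the DLT count. The estimated DLT rate goes down and the permitted dose can go up. With about 12 patients planned (Protocol 7.6), one patient carries weight.

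**Working it through.** **1. Does another passage close the gap?** Protocol 3.1 has the model updated once each patient in a cohort has had a DLT or has been observed for at least the MTD evaluation period. That is a condition on observation, not on dosing. Under Protocol 3.3.4.1, patients who stop treatment remain in the trial, subject to their agreement. A patient who stops drug early for a reason other than a DLT, or misses more than 8 doses, can therefore be followed to the end of the cycle and meet the condition in 3.1 on limited exposure.

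**2. Model and inputs** (Protocol 7.1, Table 7.1:2):

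- logit(π_d) = log α + β·log(d/8), with reference dose 8 mg and θ = (log α, log β).
- The prior is a mixture of three bivariate normals. Weight 0.8: mean (−0.94, 0.61), SD (0.91, 0.91), correlation −0.08. Weight 0.1: mean (0.85, 0.79), SD (2, 1), correlation 0. Weight 0.1: mean (−2.20, 0.80), SD (2, 1), correlation 0.
- The likelihood is the product over doses of π_d^x (1−π_d)^(n−x), for x DLTs in n patients.
- P(OD) at dose d is the posterior probability that π_d ≥ 0.33. The dose passes if P(OD) < 0.25.

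The posterior was computed by integration on a two-dimensional grid. The fineness of the grid moves the 8 mg figures below by about 0.003.

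**3. Reproducing the plan's figures.** Prior P(OD) at 4, 6, 7 and 8 mg: 0.129, 0.232, 0.310, 0.422 (Table 7.1:3 prints 0.128, 0.233, 0.310, 0.422). For Table 10.2:1:

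| Scenario | Recomputed P(OD) | Printed |
|---|---|---|
| 5 | 0.249 | 0.249 |
| 13 | 0.259 | 0.243 |
| 15 | 0.282 | 0.288 |
| 17 | 0.239 | 0.234 |
| 21 | 0.267 | 0.274 |
| 22 | 0.502 | 0.501 |

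All 18 scenarios rerun were within 0.02. Scenario 13 falls on the other side of 0.25 from the printed value, so results very close to the limit should not be pressed.

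**4. Adding one incompletely treated patient as DLT-free.** The counts are illustrative.

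| Current dose and history | Evaluable only: P(OD) | One more counted: P(OD) | Change in P(OD) | Model dose |
|---|---|---|---|---|
| 8 mg, after 0/3 at 4 mg and 0/3 at 6 mg | 2/6: 0.267 | 2/7: 0.211 | −0.056 | 7 → 8 mg |
| 8 mg, same history | 1/2: 0.314 | 1/3: 0.239 | −0.075 | 7 → 8 mg |
| 8 mg, same history | 2/5: 0.334 | 2/6: 0.267 | −0.067 | 7 mg both ways |
| 6 mg, after 1/6 at 4 mg | 2/6: 0.282 | 2/7: 0.227 | −0.055 | 4 → 6 mg |
| 6 mg, after 1/6 at 4 mg | 1/2: 0.331 | 1/3: 0.259 | −0.072 | 4 mg both ways |
| 4 mg, first dose | 1/2: 0.301 | 1/3: 0.205 | −0.096 | none → 4 mg |
| 4 mg, first dose | 2/5: 0.329 | 2/6: 0.249 | −0.080 | none → 4 mg |

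In the first row the dose choice follows in full. With 2/6, 8 mg fails and 7 mg is chosen (target-interval probability 0.454, P(OD) 0.081). With 2/7, 8 mg passes and is chosen, because its target-interval probability of 0.561 exceeds 0.429 at 7 mg.

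The pairs 2/6 and 2/7 are what the SAP 6.3 conflict could produce: seven patients treated at a dose, one of them replaced, six evaluable. Excluding the replaced patient gives 2/6 and including that patient gives 2/7. The pairs starting from 1/2 are less likely decision points, since Protocol 3.1 allows escalation on two evaluable patients only when neither has had a DLT.

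**The case against.** A reader might infer something stronger: that exclusion from the model follows the act of replacement, so the SMC puts a patient into the model simply by declining to replace. The documents do not support that.

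- Protocol 7.3.1, SAP 7.4.1 and the first sentence of the MTD Set definition make evaluability a condition of its own.
- Protocol 3.3.4.1.2 treats non-evaluability as coming before replacement. Its example of a waiver counts the evaluable patients who remain, which implies that the unreplaced patient is still non-evaluable.
- Protocol 4.1.2 mentions patients left out of DLT evaluation for reasons other than a DLT, without tying that to replacement.
- Protocol 4.2.2.1 says patients needing palliative radiotherapy in the first cycle will be replaced, so for them the permissive wording does not stand alone.
- Protocol 5.2.6.3 makes a treatment-related event requiring permanent discontinuation a DLT, so those early stoppers are counted as toxicities.

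Nor do the documents show that waivers are likely. Protocol 4.1.3 allows over-enrolment only as an exception. The sentence in SAP 6.3 may also be a slip for replacement patients, though nothing in the text says so.

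All of this stands against the stronger reading. It does not supply the missing definition: a separate condition without criteria identifies no patient, and the only list the SAP points to is the permissive one. It also leaves the contradiction in SAP 6.3 in place.

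**Conclusion.** The point holds as a gap in definition together with a direct contradiction. Evaluability governs entry to the primary model, has no stated criteria, and is referred to a list that says only who may be replaced. SAP 6.3 then includes patients whom Protocol 7.3.2 and SAP 7.8 exclude.

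In the seven configurations tried, one incompletely treated patient counted as DLT-free lowers P(OD) at the current dose by 0.055 to 0.096. In five of them that crosses the 0.25 limit and raises the model dose by a level, or opens 4 mg where no dose passed. In two it changes nothing. One crossing (0.249 at 4 mg) is too close to the limit to lean on, and so is one of the two unchanged cases (0.259 at 6 mg, printed as 0.243).

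These figures show what a misclassification would do. They do not show that one will happen, and they are not a bias estimate, since no rate of non-evaluable or unreplaced patients is given. The wording should be settled before the MTD Set is built.

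**What to change.** 1. Define MTD-evaluable in Protocol 3.3.4.1.2 and repeat it in SAP 6.3, independently of replacement and using the limits already listed. A patient is evaluable if a DLT occurred in the MTD evaluation period; this takes precedence over every other criterion, including radiotherapy. Otherwise a patient is evaluable only if the period was completed without a DLT and none of the listed conditions applies.
2. Leave all other patients out of the MTD Set whether or not they are replaced. The SMC then decides only whether to fill the slot.
3. Delete the sentence in SAP 6.3 that includes replaced patients, or reconcile it with Protocol 7.3.2 and SAP 7.8.

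It is not enough to relabel the existing list as non-evaluable. Its radiotherapy item has no exception for a DLT, so a patient with a DLT who also needed radiotherapy would drop out and a toxicity would be lost. That is why the precedence of a DLT must be written in.

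The cost is wording in both documents and possibly one fewer evaluable count in a cohort.
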